9.2. Expected adverse events related to the study intervention

Expected AEs occurring from NPA collection procedure include, by decreasing order of frequency: cough (this induced cough reflex is expected as it is the mechanism by which sample is obtained), nausea, local trauma/nose bleeding, sneezing, vomiting, and in rare cases dyspnea/low O2 saturation and heart rate deceleration <60/mm [54].

No AEs are expected from stool sample collection.

Overall, children tolerate anti-TB drugs very well when using currently recommended dosages. SAEs are rare and even mild symptoms such as nausea or vomiting are uncommon. There are occasional case reports of severe hepatotoxicity [57].

Occurrence of AEs will be monitored by study nurses and reported in the Case Report Form (CRF). Management in case of AEs will be detailed in clinical SOPs (see Chapter 7.7.1).

9.3. Reporting of adverse events

AEs occurring as a consequence of NPA collection, primary and secondary diagnosis of illness causing initial hospitalisation, death and cause of death, primary and secondary diagnosis of illness causing any hospital readmission will be reported in the CRF.

There will be no systematic reporting of other AEs in the study.

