3. STUDY ENDPOINTS

3.1. Endpoints for the primary objective

i) Sensitivity of the score obtained using predicted probability cut-off with the prediction model for the diagnosis of TB, defined as either confirmed or unconfirmed using the updated Clinical Case Definition for Classification of Intrathoracic Tuberculosis (see section 3.3)

ii) Specificity of the score obtained using predicted probability cut-off with the prediction model for the diagnosis of TB

- 3.2. Endpoints for the secondary objectives
 - 1. Proportion of confirmed and unconfirmed TB in the study population
 - 2. Clinical (symptoms, anthropometric measures, physical signs), laboratory (bacteriological, haematological, immunological signs) and radiological features (chest X-ray and abdominal US) of children with tuberculosis (confirmed and unconfirmed)
 - 3. Sensitivity and specificity of the score obtained using predicted probability cut-off with the screening prediction model for the identification of children with presumptive TB requiring further diagnostic evaluation
 - 4. Estimated time to TB treatment decision in hospitalized children with SAM, with and without presumptive TB based on the first-step screening prediction score
 - 5. Diagnostic accuracy measures (Sensitivity, specificity, negative and positive predictive value) of the different tests evaluated for the diagnosis of TB (Ultra performed on NPA and stools, CXR, abdominal ultrasound, QFT, MLR, CRP) and AUROC of diagnostic prediction models with and without the different tests results

Diagnostic accuracy of Ultra performed on NPA and stool samples will also be estimated against a specific microbiological reference standard including Ultra and mycobacterial culture from gastric aspirates (GAs)

- 6. Feasibility of NPA and stool specimen collection: proportion of children with samples collected as per study protocol
- 7. i) Safety of NPA collection procedure: adverse events (AEs) collected by study nurses (vomiting, nose bleeding, low oxygen saturation, respiratory distress)

ii) Tolerability of NPA collection procedure: discomfort/pain/distress assessed from the child (Wong-Baker face scale), by the parents (visual analog scale), by the nurses (FLACC behavioural scale) (quantitative assessment) measured in a subset of children

8. i) Mortality at 6 months, with or without TB treatment

ii) Percentage weight gain, WHZ at 6 months

- 9. TB treatment outcomes as defined per WHO recommendations [51]

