³ unable to drink or breastfeed; vomits everything; has had convulsions (more than one or prolonged >15 min); lethargic or unconscious; convulsing now [53].

- 1 NPA, collected by the nurse on the day of admission without prior nasal instillation (see Appendix 3);
- 1 stool sample, collected as soon as the child is able to produce stool (see Appendix 4);
- 2 GAs.

NPA and GAs will be done under SpO2 monitoring. They will not be attempted in children presenting severe respiratory distress or SpO2 <90% under appropriate oxygen therapy, severe dehydration or features of shock. Advice will be sought from a clinician not directly involved in the study to make the determination on a case by case basis for very sick children.

The safety of bacteriological specimen collection (NPA and GA) will be assessed by study nurses. Contraindications, implementation of sample collection procedures, and safety monitoring during collection will be detailed in study procedures.

The feasibility and tolerability of NPA will be assessed using qualitative and quantitative tools (Cf Chapter 7.6) in a sub-group of children.

Bacteriological tests performed on collected specimen are detailed in Chapter 8.2.

Additionally, a urine sample will be collected for biobanking.

Extra tests not planned by the protocol will be requested by the clinician in accordance with his/her practice and the national recommendations.

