9.4. Notification of serious adverse events

In this diagnostic study without investigational medicinal product, and with very low expected risk of AEs linked to the intervention, there will be no systematic notification of SAEs to the sponsor at the exception of:

- Death;
- Life-threatening AEs, excluding asymptomatic biological AEs of grade 4
- SAEs related to NPA collection.

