9.6. Responsibilities of the sponsor

9.6.1. SAE Recording and assessment

The sponsor shall keep detailed records of all SAEs which are reported to him by investigators.

The sponsor is responsible for the assessment of the causality of the SAE in relation to the NPA collection. In the absence of information on causality from the reporting investigator, the sponsor should consult the reporting investigator and encourage him to express an opinion on this aspect. The causality assessment given by the investigator should not be downgraded by the sponsor. If the sponsor disagrees with the investigator's causality assessment, the opinion of both the investigator and the sponsor should be provided in the report to the National Competent Authority.

All SAE for which the investigator or the sponsor considers that a causal relationship is a reasonable possibility are considered as suspected Serious Adverse Reaction (SAR).

The expectedness of the SAR shall be determined by the sponsor. The sponsor assesses if the SAE is expected or not using information described in the protocol (section 9.2), especially concerning, acts and methods performed for the research. An unexpected adverse reaction is an adverse reaction, the nature, the outcome or severity of which is not consistent with this information.

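### Section 7.4 promises a safety assessment for nasopharyngeal and gastric aspirates, but the adverse-event rules in chapter 9 cover only the nasopharyngeal aspirate

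*Protocol*

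**What the plan says.** Section 7.4 (Inclusion visit) plans one NPA, one stool sample and two GAs for each child. It treats the two aspirations alike: "NPA and GAs will be done under SpO2 monitoring", and one list of contraindications serves both. It then commits: "The safety of bacteriological specimen collection (NPA and GA) will be assessed by study nurses".

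Chapter 9 is narrower:

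- **9.1** applies the severity-grading table to events caused by NPA collection.
- **9.2** lists expected events for NPA, says none are expected from stool collection, comments on TB drugs, and does not mention GA.
- **9.3** puts into the CRF the events that follow NPA, the diagnoses behind the admission and any readmission, and death with its cause. It closes: "There will be no systematic reporting of other AEs in the study".
- **9.4** limits sponsor notification to deaths, life-threatening events (except asymptomatic biological grade 4) and "SAEs related to NPA collection".
- **9.5** has investigators grade severe or potentially life-threatening events from NPA.
- **9.6.1** says "The sponsor is responsible for the assessment of the causality of the SAE in relation to the NPA collection".

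In Table 4 the safety, feasibility, tolerability and acceptability row is marked at D0 only. The row for the two GAs is marked at D3, with conditional repeats at Months 1 and 2.

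**The concern.** A site following chapter 9 and Table 4 would not carry out the GA half of the section 7.4 commitment, and a site following 7.4 would have no reporting rule for what its nurses observe. Section 9.3 goes further than silence, because it excludes other events from systematic reporting.

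This matters because GA is not simply routine care here. Table 4 marks it as research, and as routine care only where TB is suspected. Section 8.1 describes a nasogastric tube passed in a child fasting since midnight. The shared oxygen-saturation monitoring and contraindications in 7.4 show that the authors saw a comparable need for caution. No reason is given for recording the events of one procedure and not the other.

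At stake is the safety record of a research procedure in severely malnourished inpatients. The primary endpoint is not affected.

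**Working it through.** The documents give no figure to reproduce. The check is a comparison of passages, followed by a simple count.

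**1. Which rule reaches a GA-related event?**

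| Type of GA-related event | CRF record (9.3) | Severity grading (9.1, 9.5) | Sponsor notification (9.4) |
|---|---|---|---|
| Fatal | Yes, death and cause | NPA only | Yes, any cause |
| Life-threatening, not asymptomatic biological grade 4 | No GA rule in 9.3 | NPA only | Yes, any cause |
| Leads to readmission | Yes, as readmission diagnosis | NPA only | No, unless fatal or life-threatening |
| Other SAE, such as prolonged stay or important medical event | No | NPA only | No |
| Non-serious | No | NPA only | No |

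The last two rows are wholly uncovered. The prolonged-stay case is realistic. Participants are enrolled as inpatients and the GAs are marked at D3, so an event would probably arise during the first admission. That timing is my inference. Prolonging an admission makes an event serious under 9.1, but 9.4 notifies it only if it is fatal, life-threatening or related to NPA.

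**2. Does the schedule fill the gap?** No. The one mark in the Table 4 safety row (D0) comes before the mark for the GAs (D3).

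**3. What happens to a GA event that is reported?** Under 9.6.1 the sponsor judges expectedness against section 9.2. Since 9.2 has no GA entry, there is nothing to judge it against.

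**4. How much sampling is involved?** Inputs: 1 NPA and 2 GAs per child (7.4) and 720 children (4.2).

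- Share per child: 2 / (1 + 2) = 2/3.
- Whole study: 720 × 2 = 1,440 GAs and 720 × 1 = 720 NPAs, so 1,440 / (1,440 + 720) = 1,440 / 2,160 = 67%.

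These are upper limits on planned aspirations at inclusion, before contraindications and failed collections. They include GAs that are routine care in children with suspected TB, and they leave out blood draws. They count procedures, not missed events. The documents give no GA event rate, so I put no number on missed events.

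**The case against.** The strongest reply is that much is already captured. Deaths and life-threatening events are notified whatever the cause (9.4). Cause of death and readmission diagnoses are recorded (9.3). Follow-up visits ask about any new event (7.5), and one sentence of 9.2 has nurses monitor and report events without naming NPA. Section 9.5 has investigators assess causality of all SAEs against the study intervention, and 9.1 and 9.6.2 provide a new-fact route for safety data that could change the conduct of the study. All this stands. A reader might infer that GA sampling yields no safety data, or that the IDMC and ethics committees cannot judge its risk. The documents do not support either: the IDMC sees overall safety data (14.3), and ethics committees are told of serious or unexpected events likely to affect safety (16.3). The general wording in 9.2 and 7.5 does not close the gap, however, because 9.3 is the specific reporting rule and it excludes other events.

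A second reply is that detail is left to SOPs: "Contraindications, implementation of sample collection procedures, and safety monitoring during collection will be detailed in study procedures". That is fair for how monitoring is done, but an SOP should not have to override an explicit exclusion in the protocol.

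A third is that NPA is a method under evaluation, while GA supplies the microbiological reference standard. Objective 7 and endpoint 7 are consistently NPA-only, and no objective compares the two for safety. That stands too, so the endpoint need not change.

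A reader might also note that endpoint 7(i) omits heart-rate deceleration, although 9.2 expects "in rare cases dyspnea/low O2 saturation and heart rate deceleration <60/mm". That concerns NPA, not GA, and 9.3 already records any event that follows NPA. It is an editorial difference between two lists.

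**Conclusion.** The contradiction is real and should be resolved, but its reach is limited. Section 7.4 commits to assessing GA safety, while 9.1, 9.3, 9.4, 9.5, 9.6.1 and the Table 4 safety row do not carry that out. Two things are lost:

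- systematic recording and grading of GA-related events that are not fatal, life-threatening or a cause of readmission;
- notification of GA-related SAEs that are neither fatal nor life-threatening.

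The affected procedure makes up as many as two of the three aspirations planned per child at inclusion. This rests on reading 9.3 and 9.4 as written and on the Table 4 column positions. The SOPs are not at hand and may already ask nurses for more; if so, the protocol contradicts them. The documents do not rank NPA and GA by invasiveness, and nothing here depends on such a ranking.

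**What to change.** Reconcile the passages as follows:

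- In 9.1 (severity), 9.3, 9.4, 9.5 and 9.6.1, extend the wording from NPA collection to NPA and GA collection.
- In Table 4, mark the safety row at the visit where the GAs are taken.
- In 9.2, give GA its own expected-event entry. Do not simply add GA to the NPA list: that list is ordered by frequency for NPA and describes cough as the way the sample is obtained, and 9.6.1 uses 9.2 to judge expectedness.
- Leave objective 7 and endpoint 7 limited to NPA, and report GA events descriptively.

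The cost is a protocol amendment, a CRF change and one short adverse-event form per GA, completed by nurses whom 7.4 already assigns to the assessment.

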9.4. Notification of serious adverse events

In this diagnostic study without investigational medicinal product, and with very low expected risk of AEs linked to the intervention, there will be no systematic notification of SAEs to the sponsor at the exception of:

- Death;
- Life-threatening AEs, excluding asymptomatic biological AEs of grade 4
- SAEs related to NPA collection.

9.5. Responsibilities of the investigators

The investigators are responsible for:

- Grading the severity of AEs occurring from NPA collection reported by study nurses as severe or potentially life-threatening.
- Reporting SAEs, as defined above, to the sponsor and to the appropriate country authorities, according to the procedures described in section 9.4.
- Assessing the causality of all SAE in relation to the study intervention and to concomitant intervention/medication.

The assessment on expectedness will be done by the sponsor.

SAEs, as defined above, should be reported as soon as they are known to the country CTU according to the last updated SOPs. A specific "SAE report form" will be used. SAEs will be reported immediately by the country CTU to the Inserm Pharmacovigilance Department according to appropriate SOPs. If needed, queries on SAEs will be sent to the investigators by the Inserm Pharmacovigilance Department representative.

All SAE must be reported if it occurs in a participant:

- from the date of signature of the informed consent to the study;
- during the follow-up of the participant scheduled by the study;
- until 4 weeks after the end of follow-up when it is related to the study intervention.

9.6. Responsibilities of the sponsor

9.6.1. SAE Recording and assessment

The sponsor shall keep detailed records of all SAEs which are reported to him by investigators.

The sponsor is responsible for the assessment of the causality of the SAE in relation to the NPA collection. In the absence of information on causality from the reporting investigator, the sponsor should consult the reporting investigator and encourage him to express an opinion on this aspect. The causality assessment given by the investigator should not be downgraded by the sponsor. If the sponsor disagrees with the investigator's causality assessment, the opinion of both the investigator and the sponsor should be provided in the report to the National Competent Authority.

All SAE for which the investigator or the sponsor considers that a causal relationship is a reasonable possibility are considered as suspected Serious Adverse Reaction (SAR).

The expectedness of the SAR shall be determined by the sponsor. The sponsor assesses if the SAE is expected or not using information described in the protocol (section 9.2), especially concerning, acts and methods performed for the research. An unexpected adverse reaction is an adverse reaction, the nature, the outcome or severity of which is not consistent with this information.

9.6.2. New fact reporting

When a new event is likely to affect the safety of participants, the sponsor and the investigator take appropriate urgent safety measures to protect participants against any immediate hazard.

The sponsor inform without delay the Competent Regulatory Authorities of safety data that may be relevant in terms of subject safety, or safety issues which might alter the current benefit-risk assessment of the study.

The Inserm Pharmacovigilance department shall transmit a written report to the Competent Regulatory Authorities and concerned Ethic Committee.

10. DATA COLLECTION AND PROCESSING

10.1. Description of data collected

10.1.1. Individual patient data

Once enrolled in the study, the following data will be collected for each patient by study nurses or clinician, on remote data capture devices:

- Individual identifiers: month and year of birth, sex
- Anthropometric and clinical data: weight, height, vital signs, symptoms, treatments and adherence, AEs
- Data on the tolerability of NPA collection
- Radiological and ultrasonography data: digital images and interpretation
- Laboratory data: mycobacterial culture and Ultra assay, HIV testing, QFT, blood tests
- Samples collected for biobanking
- Management of SAM: antibiotics, nutritional support, other
- TB treatment if initiated
- Comorbidity management: antiretroviral treatment, other
- Outcome data: end of study status or early study termination (death, lost to follow-up, withdrawal)

For each new patient included in the study, an anonymised individual identification code will be attributed and used as the only patient identifier in the REDCap database.

10.1.2. Cost data

We will collect data to estimate the costs of the TB diagnostic approaches being compared. This will include the costs of TB diagnostics, including collection and testing of samples, and the other direct health costs required to treat patients, including treatment for SAM, TB and other comorbidities, use of equipment and staffing costs.

We will measure and record, or where necessary estimate, resource utilization for both use of the new diagnostic prediction score and standard of care in children hospitalized with SAM. Unit costs will be collected from relevant sources including clinic and hospital site visits, accounts and invoices from the TB-Speed project and individual facilities, pharmaceutical and medical equipment manufacturers, Ministries of Health and NTPs.

To estimate human labour costs, we will conduct a time and motion study survey to estimate quantities of staff time involved in different health care tasks. To do so, we will ask nurses, doctors and other health workers participating in this study to self-complete timesheets recording the length of time they spend conducting each task.

Costs will be expressed in U.S. dollars, converted using purchasing power parity exchange rates, i.e. market exchange rates adjusted for differences in purchasing power between countries.

10.2. Definition of source data

Source data must be available to document the existence of patients enrolled in the study and should substantiate integrity of the data collected. It must include the original documents relating to the study, the medical treatments and medical history of the patient.

The following information should be collected from source medical records filled by site physicians:

- Patient's demographic data (month and year of birth, sex)
- Study name(s) and protocol number(s) in which the patient participates
- Details related to the inclusion criteria
- Date of signing informed consent form
- Dates of follow-up visits
- Medical history and physical examination details
- Laboratory print-outs
- AEs and concomitant treatments

For the purpose of the study, specific forms may be developed for source data collection to be inserted into medical records.

In addition to the source medical records, radiological data will be collected as digital imaging and communications files (.dicom files). CXRs interpretation will be directly reported in the patient's CRF using standardized forms developed as part of the study.

In the same way, Ultra test result files (.gxx files) will be extracted directly from the GeneXpert software.

Data transfer for dicom and gxx files is detailed in Chapter 10.3.6.

10.3. Electronic data entry

The eCRF system, the methods to ensure restricted access to the database, and the data management procedures, including the procedures to check completeness, accuracy, quality and validity of the data, will be described in specific trial SOPs in accordance with good clinical, scientific and data management principles.

10.3.1. eCRF

A real time data collection is needed for optimised monitoring of data entry. No paper CRFs will be used; patient data collected at inclusion and follow-up visits will be recorded directly in an electronic CRF (eCRF) by study nurses, mostly through single data entry.

The TB-Speed data management system will be based on the electronic data capture application REDCap (Research Electronic Data Capture; https://www.project-redcap.org/). REDCap is an online tool for eCRF development, allowing data input from anywhere in the world over a secure connection with authentication and data logging.

Design and conception of the eCRF will be done by the international trial manager in close collaboration with the international data manager and international Clinical Research Assistant (CRA).

10.3.2. Data hosting

The REDCap MySQL database server will be hosted by the international CTU at the University of Bordeaux (UBx), France. REDCap is a free, secure web application for building and managing online surveys and databases, it's geared to support online and offline data capture.

Developed by Vanderbilt University, the REDcap software complies with internationally recognized standards including the Health Insurance Portability and Accountability Act (HIPAA, 1996), the United States legislation providing data privacy and security provisions for safeguarding medical information, as well as part 11 of Title 21 of the Code of Federal Regulations (CFR) that establishes the United States Food and Drug Administration (FDA) regulations on electronic records and electronic signatures.

10.3.3. Data security

The eCRF will be accessible 24/24h by secure authentication to a restricted users group. The connection will be authenticated by a user ID, password and digital certificate enabling data encryption during transfer and storage to the central server. Access and rights levels will be granted and managed by the international data manager (international CTU).

The server hosted at UBx will be saved every weekend on a hard drive, and send to bands (rotation frequency of the bands will be every five weeks). The database will be saved incrementally on a hard drive every working day.

[figure not shown]
